Demographic Evaluation	X					
Surgical & Discharge Information		X				
Physical Exam	X		X	X	X	X
Physician Assessment of Postop Radiographs		X	X	X	X	X
Subject completed:						
Forgotten Joint Score (FJS-12)	●		●	●	●	●
Oxford Knee Score (OKS)	●		●	●	●	●
UCLA Activity & Satisfaction Survey	●		●	●	●	●
Site completed as applicable:						
Adverse Event Report		★	★	★	★	★
Protocol Deviation	★	★	★	★	★	★
Study Completion	★	★	★	★	★	★
Explanted Device Form			★	★	★	★

Activity	Preop	Immediate Postop	6 Weeks Postop	6 Months Postop	1 Year Postop	2 Years Postop
Radiograph Submission		X	X	X	X	X

- X Site completed (Investigator or designee)
- Subject completed
- ★ Site completed as applicable (Investigator or designee)

The following table indicates required forms to be completed by the site for revision patients:

Form Name	Comments
Physician Assessment of Postop Radiographs	Mark the “Pre-Revision” exam period.
Adverse Event Report	Document adverse event resulting in the revision.
Study Completion	Complete indicating “Study Prosthesis Removed” under Study Completion Status.
Explanted Device Form	Document explanted device information. Send explanted device to Zimmer Biomet per Appendix F.
Medical Device Reporting Information Form (MDRIF):	If device-related, complete MDRIF form (Appendix E) and forward the form and all applicable supporting documents to Zimmer Biomet within 7 days. The supporting documents include: 
 ▪ Operative reports (index and revision surgery) ▪ Radiographs (immediate postop, intermediate, and pre-revision)

IV. Introduction and Purpose

In recent years the advent of highly porous trabecular metal implants in cementless fixation has brought the cemented vs. cementless debate back to the forefront among surgeons when determining best practices and benefits to patients. Fricka, et al [3], describe the potential benefits of cementless fixation as preservation of bone stock, shorter operating room time (and thus a cost savings), ease of revision if necessary, and elimination of any complications associated with cemented fixation such as third body wear and retained loose fragments. Potential disadvantages are the lack of surgeon experience implanting the modular tibial tray, cost of such implants, and determining if there is an ideal patient population for implantation of such devices.

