To address clinical challenges and methodologically address implant characteristics, a prospective, multi-center, longitudinal data collection model is being proposed for *NexGen TM* Tibia components used in primary cementless tibia total knee arthroplasty.

V. Study Objectives

The primary objective of this study is to evaluate clinical performance for the commercially available *NexGen TM* Monoblock Tibia and *NexGen TM* Modular Tibia used in primary cementless tibia total knee arthroplasty. This will be done by analysis of radiographic parameters and validated patient report outcome measurements as well as monitoring adverse events and survivorship of the implant.

The assessments will include:

1. Clinical performance measured by radiographic parameters, pain and function, and survival of the device.
2. Safety based on incidence and frequency of adverse events.

VI. Study Design

This is a prospective, multicenter, non-randomized clinical study designed to facilitate the collection and evaluation of radiographic parameters, pain and function, survival of the device, and adverse event data. This clinical study will include the *NexGen TM* Monoblock Tibia and *NexGen TM* Modular Tibia as 2 single-arms being analyzed separately.

The primary endpoint of this study is to evaluate the clinical performance of the implant at 2 years postoperatively using radiographic parameters. Radiographs will be assessed for the absence of progressive tibial radiolucencies, as defined in the radiographic protocol.

The secondary endpoints of this study will evaluate the clinical performance of the implant at 2 years postoperatively, based upon:

- No revisions for any reason
- Oxford Knee Score >38

A minimum of 132 subjects are to be enrolled in this study, with approximate equal distribution of at least 66 *NexGen TM* Monoblock and 66 *NexGen TM* Modular subjects. A maximum of 10 U.S. sites will contribute, each enrolling between 22 to 30 implanted knees. Each site will be selected for a specific *NexGen TM* device, either the Monoblock or Modular design.

Investigators will be skilled in cementless total knee arthroplasty and experienced implanting either the *NexGen* TM Monoblock Tibia or the *NexGen* TM Modular Tibia.

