Each Principal Investigator will be responsible for obtaining Institutional Review Board (IRB) approval as required prior to conducting the study. In order to avoid potential selection bias, each Investigator will offer study participation to each consecutive eligible patient presenting as a candidate for primary cementless tibia total knee arthroplasty using the *NexGen* TM Monoblock or *NexGen* TM Modular Tibia. Eligible candidates who express interest in study participation will be offered Informed Consent. All potential study subjects will be required to participate in the Informed Consent process and will not be considered enrolled in the study until the candidate has signed and dated the IRB approved Informed Consent Form. Study data cannot be collected until the candidate has completed the Informed Consent process and signed and dated the IRB approved Informed Consent Form.

All study subjects will undergo preoperative clinical evaluations prior to their cementless tibia total knee arthroplasty. An immediate postoperative radiograph will be required. Postoperative clinical follow-up and radiographic evaluations will be conducted at 6 weeks, 6 months, 1 year, and 2 years.

The Investigator will review radiographs immediately postop and at each clinical evaluation to ensure the radiographs meet the protocol requirements. The Sponsor will provide a radiographic protocol (Appendix D) to assist sites in proper x-ray technique in order to assure adequate images are captured for study analysis.

The Sponsor will request copies of these radiographs for independent radiologic review. The Sponsor will request one central reviewer for all radiographs independent of the surgeon and institution.

VII. Study Population

The study population for primary statistical analysis will be comprised of subjects who require primary cementless tibia total knee arthroplasty and satisfy the inclusion/exclusion criteria outlined in this section of the protocol. In order to avoid potential selection bias, Investigators will offer study participation to each consecutive eligible patient presenting as a candidate for primary cementless tibia total knee arthroplasty using the commercially available *NexGen* TM Monoblock or *NexGen* TM Modular Tibia implants. Eligible candidates who express interest in study participation will be offered Informed Consent. The **Inclusion/Exclusion Criteria** should not be completed until the study-specific Informed Consent Form has been completed.

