Clinical Interval	Interval Window in Days Postop*	Approximate Window in Weeks or Months Postop
6 weeks	28 to 56 days	± 2 weeks
6 months	151 to 214 days	± 1 month
1 year	333 to 396 days	± 1 month
2 years	669 to 791 days	± 2 months

*Visit(s) outside of window will be determined based on Days Postop

Postoperative follow-up clinical data will be collected on the following source document forms:

1. Physical Exam
2. Physician Assessment of Postop Radiographs
3. Forgotten Joint Score
4. Oxford Knee Score
5. UCLA Activity & Satisfaction Survey
6. Adverse Event Report (as applicable)
7. Protocol Deviation (as applicable)
8. Study Completion (as applicable)
9. Implanted Device Form (as applicable)

Subjects will be followed postoperatively for 2 years. Unless the study is otherwise closed, data will continue to be collected until the subject completes the study per the protocol, voluntarily withdraws from the study, is withdrawn from the study by the investigator, is lost to follow-up, undergoes revision to remove a study device, or expires. See Management of Incurrent Events (Section X, Subsection D of this protocol) for additional details. Reason(s) for study completion must be documented on the **Study Completion** form.

K. Minimization of Subjects Lost to Follow-up

Subject follow-up is extremely important for the conduct of a clinical study, and the expectation is to maintain the highest possible rate of follow-up compliance throughout this study. During the informed consent process and at each follow-up interval, subjects should be counseled on the importance of completing future study follow-up intervals.

L. Radiographic Definitions and Methods

All postoperative radiographs will be evaluated by the Investigator and documented using the **Physician Assessment of Postop Radiographs**. An **Adverse Event Report** must be completed for findings identified as an adverse event.

It is the Investigator's responsibility to review radiographs for image quality during the subject's clinical visit and prior to uploading into the image collection service. Radiographic images must show an orthogonal view of the tibial implant interface. If the Sponsor determines a radiograph is of poor quality, then the site must reschedule the subject for additional radiographs.

1. Required radiographic views

Radiographic Interval	Interval Window	Required Radiograph
Immediate Postop	Pre weight-bearing	AP and Lateral
6 weeks	± 2 weeks	AP and Lateral

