Adverse Events, Serious Adverse Events, Adverse Device Effects, and Serious Adverse Device Effects will be documented on the **Adverse Event Report** throughout this study, including information on the date of onset, treatment and resolution, as well as assessment of both the seriousness and the relationship to the study device. The outcome of complications will be documented and changes in outcome are to be updated during the course of the study. In case of early termination of this study, further follow-up of the subject shall proceed according to the hospital's standard procedure.

Device Deficiencies that did not lead to an adverse event but could have led to a medical occurrence if suitable actions had not been taken, if intervention had not been made, or if circumstances had been less fortunate, shall be reported to the Sponsor as soon as possible, as well.

See Section X, Subsection E of this protocol for additional information regarding adverse event classifications. All medical events, regardless of classification, are required to be reported on the **Adverse Event Report**. The completed **Adverse Event Report** must be submitted to the Sponsor in a timely manner. The Investigator or Designee will also promptly provide the Sponsor with any additional requested information required for the Sponsor to comply with regulatory requirements. If applicable per their reporting requirements, the Investigator or Designee will also report applicable adverse event(s) to their IRB.

3. Revision

Study subjects will be study completed for any revision, regardless of the component being revised. In the event that removal of one or more of the implanted knee components is necessary, the Investigator will determine the best treatment and/or revision method for the subject.

Prior to revision surgery, the Investigator or qualified Designee must document radiographic findings on the **Physician Assessment of Postop Radiographs**.

Once the revision surgery has been completed, the Investigator or qualified Designee must complete an **Adverse Event Report** as well as a **Study Completion** form terminating the subject from the study. For the study completion status, select "Study Prosthesis Removed".

All explanted device information must be documented on an **Explanted Device Form**. In addition, all explanted devices must be returned to Zimmer Biomet using the **Explant Procedure** (Appendix F).

4. Investigator Withdrawal

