NOTE: The term “severe” refers to the intensity of the event and can be used with any event, without regard to whether or not it meets the criteria for being classified as “serious” or “unanticipated”. For example, a subject can have a severe headache, but it is not a serious event.

3. Relation to Device

Not Related:

There is no possible relationship between the adverse event and the implanted device.

Uncertain:

It is not known if there is a possible relationship between the adverse event and the device.

Probably:

There is a reasonable possibility that the adverse event was caused by the device.

Definitely:

There is no doubt the adverse event is directly related to the device.

Medical Device Information Reporting

For any adverse event with a relation to device of “Uncertain”, “Probably” or “Definitely”, a **Medical Device Reporting Information Form** (MDRIF, Appendix E) must be completed and submitted to the Study Manager within 7 days. Other required supporting documentation that should be sent with the MDRIF:

- All subject x-rays
- Operative notes
- A summary detailing the subjects postoperative physical therapy regimen
- Subject activity level at the time the event occurred.

4. Outcome Definitions

The outcome is in relationship to the Adverse Event, not the treatment rendered for the event (if any).

Resolved:

The adverse event has been resolved and/or no further treatment is required to treat the reported condition or illness.

Tolerated:

The adverse event will most likely never be resolved. The subject “tolerates” the illness or condition as a matter of life.

Pending:

Treatment or diagnostic studies were prescribed for the adverse event and the outcome of the adverse event is not yet known.

Study Withdrawal:

Due to the adverse event, the subject was withdrawn from the study.

Device Revision/Removal:

The adverse event resulted in the removal of a study device.

Death:

The outcome indicates the subject died as a direct result of the reported adverse event.

Reoperation of Affected Joint:

The adverse event resulted in reoperation of the study joint, but the reoperation did not include removal of a study device.

5. Collection Approach

The type of approach taken to collect adverse event information, whether systematic or non-systematic.

Systematic:

Based on checklists, questionnaires, or tests

Non-Systematic:

Based on spontaneous reporting and recording

F. Monitoring of the Study

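### Does the lack of a stated rule for knees revised before 2 years bias the primary radiographic success rate?

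*Combined protocol and SAP*

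**What the plan says.** Section VI sets the endpoint in two sentences: "The primary endpoint of this study is to evaluate the clinical performance of the implant at 2 years postoperatively using radiographic parameters" and "Radiographs will be assessed for the absence of progressive tibial radiolucencies, as defined in the radiographic protocol". The radiographic protocol is Appendix D, which is not part of the text reviewed. Revision is a separate secondary endpoint, "No revisions for any reason", and Section XII.A adds a Kaplan-Meier summary of implant survival.

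Section X.D.3 closes the case at revision: "Study subjects will be study completed for any revision, regardless of the component being revised". Sections IX.J and X.D.8 put it a little differently, listing a subject who "is lost to follow-up, undergoes revision to remove a study device, or expires" among those whose participation ends. Section IX.J sends the reader to Section X.D for details.

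On the denominator, Section VII says: "The study population for primary statistical analysis will be comprised of subjects who require primary cementless tibia total knee arthroplasty", subject to the eligibility criteria. Nothing there removes a knee for lacking a 2-year film.

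On data, Sections III and X.D.3 require a radiographic assessment before any revision. Section IX.L.2 has all radiographs submitted to the sponsor and the postoperative study films read independently, and Section VI provides for one central reviewer. For events whose device relation is uncertain, probable or definite, Section X.E.3 also asks for "All subject x-rays".

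Section XII makes descriptive summaries the basis of all reports. The 98% performance goal and 10% margin appear only in the sample-size paragraph, XII.B.

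**The concern.** A tibia revised for loosening is the clearest fixation failure this endpoint could meet, and it is also a knee that will never have a 2-year study film. If the rate were computed only among knees with that film, missingness would depend on the outcome: the worst failures would drop out, and the figure would become success among knees still unrevised.

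The design leaves little slack. With 57 evaluable knees, the bound implied by XII.B tolerates one or two failures, so a single dropped knee could change whether an arm appears to meet it. Section XII contains no rule for a revised knee, a missing 2-year film or the denominator, so nothing in the text reviewed expressly rules this reading out.

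**Working it through.** **Inputs from XII.B.** Expected success 98%; goal 98%; margin 10 points, so the implied null is 98% − 10% = 88%; power 80%; alpha 0.05, sidedness not stated; 57 evaluable and about 66 enrolled per arm; 12% loss. The revision rate (v) and the share of revisions that are true radiographic failures (f) are not in the documents and are assumed below.

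**The plan's own figure.** One-sample proportion, normal approximation:

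n = [(z_α·√(0.88×0.12) + z_β·√(0.98×0.02)) / 0.10]²

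- One-sided 0.025 (two-sided 0.05): [(1.960×0.3250 + 0.8416×0.1400)/0.10]² = 56.96, so 57, as stated.
- One-sided 0.05: 42.6, which does not match.

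The stated 57 therefore corresponds to one-sided 0.025. Enrolment: 57/0.88 = 64.8, so 65, close to the stated 66.

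**Failures tolerated among 57 knees (exact binomial, null 88%).** P(X≤1) = 0.0060, P(X≤2) = 0.0263, P(X≤3) = 0.0771. One failure is allowed at one-sided 0.025 and two at one-sided 0.05.

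**Effect of one dropped knee.**

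| Result | Rate | Exact p against 88% | At 0.025 | At 0.05 |
|---|---|---|---|---|
| 55/56 | 98.2% | 0.0067 | meets | meets |
| 55/57 | 96.5% | 0.0263 | misses | meets |
| 54/56 | 96.4% | 0.0290 | misses | meets |
| 54/57 | 94.7% | 0.0771 | misses | misses |

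At the level that reproduces 57, the pair that flips is 55/56 against 55/57. The pair 54/56 against 54/57 flips only at one-sided 0.05.

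**False-pass probability if revised knees are left out.** True success 88%, 57 filmed knees. Failure rate among filmed knees = (0.12 − f·v)/(1 − v). For f = 1 and v = 0.03 this is 0.09/0.97 = 0.0928, an apparent success of 90.7%.

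| f | v | Apparent success | One-sided 0.025 | One-sided 0.05 |
|---|---|---|---|---|
| – | 0 | 88.0% | 0.6% | 2.6% |
| 1 | 1% | 88.9% | 1.0% | 4.0% |
| 1 | 3% | 90.7% | 2.7% | 9.1% |
| 1 | 5% | 92.6% | 7.1% | 19.9% |
| 0.5 | 1% | 88.4% | 0.7% | 3.2% |
| 0.5 | 3% | 89.2% | 1.2% | 4.6% |
| 0.5 | 5% | 90.0% | 1.8% | 6.7% |

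At one-sided 0.025, four of the six scenarios stay below nominal, one is barely above (2.65%), and one is material (7.1%). With f = 0.12, the overall failure rate, there is no bias.

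**At the planned 98%.** With 1% revised, apparent success is 1 − (0.02 − 0.01)/0.99 = 99.0% if all revisions are failures, and 98.5% if half are. The overstatement is at most 1 point. All-failure revision rates of 3% or 5% cannot occur when only 2% of knees fail.

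**Which reading the text supports.**

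- Section VII defines the primary population by eligibility, so a revised knee stays in it.
- Progression is a comparison across films, and a revised knee has its immediate postoperative film, any scheduled films before revision, and a required pre-revision assessment.
- Section IX.L.2 routes films to independent review whether or not the subject later completes 2 years.
- No section limits the analysis to knees with a 2-year film.

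**The case for a change.** The best case for a change is that a descriptive rate needs a denominator as much as a test does. Section XII allows the summaries to support regulatory submissions and publications, and XII.B sizes the study on a non-inferiority comparison of this very rate. Showing revisions in a secondary endpoint does not correct the primary figure. A scoring rule would cost one paragraph and is best fixed before outcomes are known. Section X.D.3 also directs one completion status for every revision, so that field alone cannot separate a loose tibia from another cause.

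Much of this stands. The text reviewed contains no scoring rule, and the arithmetic of the film-only reading is right. The gap is also wider than the primary rate: an Oxford Knee Score above 38 at 2 years has no value for a revised knee either. Pre-revision films are not a listed interval in Section IX.L, so whether the general submission rule reaches them is a matter of interpretation.

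What does not stand is the step from missing detail to a biased result. That step needs an analyst to choose a reading that no section states, to set aside required pre-revision findings, and to ignore the adverse event and explant forms, which can supply the reason for revision and the component removed. It also assumes that Appendix D, where the endpoint is defined, is silent. Section VI describes that appendix mainly as help with x-ray technique, so a scoring rule there is not assured, but its absence cannot be shown from the text reviewed.

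**Conclusion.** No change to the plan follows. The plan leaves a detail unwritten, and the sections around it point to the sensible answer: keep the knee in the eligible population and judge it on its serial and pre-revision films.

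The potential harm is bounded. It arises only under an unstated film-only reading, and the 88% bound is not a planned decision rule in the analysis section. At one-sided 0.025 the false-pass probability becomes material, at 7.1%, only when 5% of knees are revised, every one is a true radiographic failure, and true success sits exactly at 88%. At the planned 98% with 1% revised, the overstatement is at most 1 point. Revisions remain visible in the secondary endpoint and the survival curve, so a reader could see that failures had left the primary rate.

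These sizes rest on assumed revision rates of 1% to 5%, assumed failure shares of one half or all, and 57 filmed knees. The differing phrases in X.D.3, IX.J and X.D.8 about which revisions end participation are a wording matter and do not alter this conclusion.
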